#### 7.1.4. Strategy for Intercurrent (Post-Randomisation) Events

Intercurrent Event	Primary Estimand	Secondary Estimand
Study treatment discontinuation due to an AE/SAE	Excluded from analysis	Set as loss of asthma control (i.e. worst case scenario).
Death	Excluded from analysis	Set as loss of asthma control (i.e. worst case scenario).
Prohibited/ Concomitant medications that could impact patients' asthma control	Use data as is.	Set as loss of asthma control (i.e. worst case scenario).
Non-compliance with FP/SAL, FP or study titration	Use data as is.	Set as loss of asthma control (i.e. worst case scenario).
Missing data *	Excluded from analysis	Set as loss of asthma control (i.e. worst case scenario).
Notes:		

 
• * Missing data is not an intercurrent event, however missing values will be imputed according to the estimand under investigation.
 
		

- |  |
|--|
| 
 
• If the intercurrent event occurs after loss of asthma control then all information on loss of asthma control will be used.
 
• Prohibited/ concomitant medications will be identified as protocol deviations within the prohibited/ concomitant medications category and will have text that start with “LoAC”
 
• Non-compliance FP/SAL, FP or study titration will be identified as compliance <80%, compliance ≥ 120% or protocol deviations within the other deviations related to wrong study treatment/administration/dose sub-category and will have text that starts with “TIT”
 
 |
|--|

If any of the following intercurrent events occurs, then all data will be accepted:

- Pregnancy  
Accidental unblinding

Whilst it’s possible that site staff were unable to administer study drug as they were unable to find a suitable vein, the team felt this would not be caused by the randomised study treatment and the visit would be rescheduled. Therefore, if this occurs all data will be accepted and treated as any other out of window assessment.

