**7.2.3. Strategy for Intercurrent (Post-Randomisation) Events**

For the analysis of time to loss of asthma control, both primary and secondary estimands (Section 7.1.4) will be examined. It is important to assess both estimands as data is missing after withdrawal or loss of asthma control. This could produce biased estimates, as loss of control and therefore missing data is related to study treatment, and so the secondary estimand where missing data is set as non-responders must also be considered.

For all other endpoints, only the primary estimand will be examined. This estimand uses all data as collected, except for data collected after the date of loss of asthma control or early withdrawal from study treatment.

Once participants experience loss of asthma control and/or withdraw from study treatment they immediately restart their standard of care medication (ICS/LABA). As a

result, any data collected past this point will have been impacted by the standard of care medications and any estimates produced biased by the additional use of ICS/LABA. For this reason, data post withdrawal from study treatment is not included in the on-treatment efficacy analysis.

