**7.2.4.1. Statistical Methodology Specification**

Endpoint / Variables

 
Time to loss of asthma control.
 

Strategy for Intercurrent (Post-Randomisation) Events

 
Both primary and secondary estimands (Section 7.1.4) will be examined. It is important to assess both estimands as data is missing after withdrawal or loss of asthma control. This could produce biased estimates, as loss of control and therefore missing data is related to study treatment, and so the secondary estimand where missing data is set as non-responders must also be considered.
 

Model Specification

 
Time to loss of asthma control will be analysed on the Modified Intent-to-Treat excluding GCP non-compliant subjects (Loss of Control) population using Kaplan-Meier analysis (Proc lifetest). Within the Kaplan Meier plot participants will either be counted as an event or they will be censored.
 
A log rank test will be performed to test for difference between the time to loss of asthma control on Placebo compared with GSK3772847
 
 
Primary Estimand:
 
 
Events: Participants who experience loss of asthma control during the study
 
Censoring: Participants who discontinue investigational product for reasons other than loss of asthma control will be censored at the date of early withdrawal from study treatment. Participants who successfully complete the 16 week treatment period will be censored at 113 days (16 weeks + 1 day).
 
 
Secondary Estimand:
 
 
Events: Participants who experience loss of asthma control during the study or who discontinue investigational product for reasons other than loss of asthma control (date of event will be set to date of early withdrawal from study treatment).
 
Censoring: Participants who successfully complete the 16 week treatment period will be censored at 113 days (16 weeks + 1 day).
 

Time to event/censoring = Date of event/censoring – Treatment start date + 1. If participants experience multiple reasons for loss of control then the earliest date will be used as described in Section 0.

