Procedure	Pre-Screening 	Screen Run-in	Treatment Period										Follow-up Period  (± 3 days)			Notes
			± 2 days			± 3 days							12	13	14	
Visit	0	1	2 	3	4	5	6	7	8	9	10	11 (ETP or EW)	12	13	14	1. Pre-screening and screening can occur on the same day 2. FU period to start 4 weeks after ETP or EW visit. 3. Visit 2 = Day 1 (first dose of IP).
Week	-4~-2	-2	0	1	2	4	6	8	10	12	14	16	20	24	28	
Study Day	-28~-14	-14	1	8	15	29	43	57	71	85	99	113				
Genetic blood sample – Pre dose							X									Pharmacogenetic sample may be drawn any time from Visit 2 onwards. Informed consent for optional substudies e.g. genetics must be obtained before collecting a sample
Sputum sample collection			X					X				X				Pre-dose collection and in a sub-set of participants (~50 %) at selected sites; also collected for EW participants
PK, target engagement and immunogenicity assessments			X	X	X	X		X		X		X	X	X	X	See SoA Table 2 for details
Exploratory Biomarkers			X					X				X				Pre dose collection
Efficacy																
Spirometry		X	X		X	X	X	X	X	X	X	X				Test to be performed pre-dose during the Treatment period
Reversibility		X														
FeNO			X	X	X	X	X	X	X	X	X	X				Test to be performed pre-dose
Review loss of asthma control criteria				X	X	X	X	X	X	X	X	X				It will include review of data to determine loss of asthma control. See Section 9.1.5.
Dispense eDiary		X														

Procedure	Pre-Screening 	Screen Run-in	Treatment Period										Follow-up Period  (± 3 days)			Notes
			± 2 days			± 3 days							12	13	14	
Visit	0	1	2 	3	4	5	6	7	8	9	10	11 (ETP or EW)	12	13	14	1. Pre-screening and screening can occur on the same day 2. FU period to start 4 weeks after ETP or EW visit. 3. Visit 2 = Day 1 (first dose of IP).
Week	-4~-2	-2	0	1	2	4	6	8	10	12	14	16	20	24	28	
Study Day	-28~-14	-14	1	8	15	29	43	57	71	85	99	113				
Collect eDiary												X				
Review eDiary			X	X	X	X	X	X	X	X	X	X				
Safety																
12-lead ECG		X	X 			X 		X 		X 		X				1. Test to be performed pre-dose and post-dose within 30 mins after end of infusion.
24 hrs Holter		X	X 			X 				X 						Holter monitor needs to be returned to clinic at end of 24-hour recording (i.e. the next day). 1. Place the Holter 30-60 mins prior to dosing.

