### 12.6.2. Study Population

Age
Date of birth will be set as PPD YYYYY where YYYYY is the year of birth taken from the CRF. For participants who attended a screening visit, age will be calculated at the screening visit date. For pre-screen failures, age will be calculated at the pre-screening visit date.
Body Mass Index (BMI)
BMI = Weight (kg) / Height(m) 
Treatment Misallocations
To allocate treatment, the number of doses of GSK3772847 and Placebo that were given will be calculated, and the subject will be assigned to whichever treatment has the higher number. The only exception will be when both treatments were given equally, in which case the subject will be assigned their randomised treatment.
Early Withdrawal from Study Treatment Date

The eCRF captures the study treatment start and end, however this is the physical time and date of the infusion. The date of early withdrawal from study treatment is not captured and should therefore be calculated as follows:
 
 
• If the participant withdrew from treatment due to loss of asthma control then the date of early withdrawal from study treatment is set to the date of loss of asthma control.
 
• If the participant withdrew due to an AE/SAE/Death then withdrawal date is set to the AE/SAE onset date (all deaths should be reported as serious adverse events)
 
• If the participant withdrew from study treatment (for a reason other than those above) during the first 10 weeks of the study i.e. during the down titration of the background medications, then the FP/SAL or FP discontinuation date should be used as the date of withdrawal from study treatment.
 
• For participants who withdraw from study treatment (for a reason other than those above) between Week 10 and Week 16, there is no information on when they withdrew as they are no longer taking background medications. The date of early withdrawal from study treatment should therefore be set to the maximum of date of last dose of FP and date of last dose +1. This is because no more information is available other than the fact that they had not lost control prior to completing the down titration or prior to receiving their final dose of IP.
 

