**Treatment Compliance for Fluticasone Propionate (FP) and Salmeterol (SAL)**

- Treatment compliance will be calculated based on the formula:  

$$\text{Treatment Compliance} = \frac{\text{Number of Actual Doses}}{(\text{Planned Treatment Duration in Days} * \text{Frequency})} * 100$$
- Frequency is 2 for BID and 1 for QD. Treatment compliance could be greater than 100% if there are events of overdose. Cumulative compliance (since Day 1) by each background therapy will be calculated.
- Planned Treatment Duration is defined according to the schedule of activities.
- Compliance will be summarized by the following categories:  
 <80%,  
 ≥ 80% to < 95%,  
 ≥95% to <105%,  
 ≥ 105% to <120% and  
 ≥120%

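### The time-to-event version of the worst-case estimand omits two situations that Section 7.1.4 sets to loss of control

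*SAP*

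**What the plan says.** All references are to the amended RAP.

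- **Section 7.1.4** lists five situations: study treatment discontinuation for an AE/SAE, death, "Prohibited/ Concomitant medications that could impact patients' asthma control", non-compliance with FP/SAL, FP or the titration, and missing data. The secondary-estimand entry is the same for all five: "Set as loss of asthma control (i.e. worst case scenario". Notes to the table identify the medication deviations by a LoAC text prefix. Non-compliance is identified by compliance below 80% or at least 120%, or by a TIT text prefix.
- **Section 7.2.3**: "For the analysis of time to loss of asthma control, both primary and secondary estimands (Section 7.1.4) will be examined". Section 7.2.4.1 repeats this: "Both primary and secondary estimands (Section 7.1.4) will be examined".
- **Section 7.2.4.1** then defines secondary-estimand events as "Participants who experience loss of asthma control during the study or who discontinue investigational product for reasons other than loss of asthma control". Participants who complete the 16 weeks are censored at 113 days. Everyone is to be either an event or censored.
- **Section 12.6.2** dates withdrawals between Week 10 and Week 16, for reasons other than loss of control or AE/SAE/death, at the later of the last FP dose and the last dose plus one day. The reason given is that "there is no information on when they withdrew as they are no longer taking background medications".
- **Section 12.2.1** schedules a loss-of-control review at every treatment visit after Day 1, including Week 14. Its note reads "It will include review of data to determine loss of asthma control".

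**The concern.** Table 2.13 reports the probability of loss of control by 16 weeks, and a reader will set it beside the 16-week worst-case proportions in Tables 2.6 and 2.7. All three carry the label Secondary Estimand, but they rest on different event sets. The Kaplan-Meier version leaves two of the five worst-case situations as non-events, so it is less conservative than its name says and cannot be reconciled with the binary result it is meant to support. A programmer following 7.1.4 and one following 7.2.4.1 would produce different curves.

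The dating rule is a lesser matter. It moves some event and censoring times earlier than the scheduled assessments require.

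**Working it through.** **1. The plan's own figure.** Completers are censored at 16 × 7 + 1 = Day 113. The exposure formula in 12.6.2 agrees: with the last dose on nominal Day 85, 85 − 1 + 29 = 113.

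**2. Side by side, secondary estimand.**

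| Situation in 7.1.4 | Binary (Tables 2.6, 2.7) | Kaplan-Meier (Table 2.13, Figure 2.10) |
|---|---|---|
| AE/SAE discontinuation | failure | event |
| Death | failure | event (as a discontinuation) |
| Prohibited/concomitant medication, treatment completed | failure | not listed; censored at Day 113 |
| FP/SAL, FP or titration non-compliance, treatment completed | failure | not listed; censored at Day 113 |
| Missing data | failure | event if treatment was discontinued |

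**3. Size.** The inputs are 70 per arm and planning proportions of 44% (placebo) and 28% (GSK3772847), from Section 2.6. As a check on that section, 1 − 0.28/0.44 = 36.4%, which agrees with its stated 36%. The share q of event-free completers with either deviation is not in the SAP. It is assumed to be 2% to 20% and equal in both arms. For illustration, everyone without loss of control is taken to complete.

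Binary worst-case proportion = p + (1 − p)q. The Kaplan-Meier proportion stays at p. Gap in participants = 70(1 − p)q.

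| q | Placebo: proportion, gap | GSK3772847: proportion, gap | Ratio of proportions |
|---|---|---|---|
| 0 (Kaplan-Meier as written) | 44.0%, 0 | 28.0%, 0 | 0.280/0.440 = 0.64 |
| 2% | 45.1%, 0.8 | 29.4%, 1.0 | 0.2944/0.4512 = 0.65 |
| 5% | 46.8%, 2.0 | 31.6%, 2.5 | 0.316/0.468 = 0.68 |
| 10% | 49.6%, 3.9 | 35.2%, 5.0 | 0.352/0.496 = 0.71 |
| 20% | 55.2%, 7.8 | 42.4%, 10.1 | 0.424/0.552 = 0.77 |

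**4. Withdrawal date, nominal days.** For a participant infused at Week 12 (Day 85), the last FP dose is about Day 71, so the derived date is max(71, 85 + 1) = Day 86. The latest withdrawal short of completion is Day 112, and 112 − 86 = 26 days. The Week 14 review on Day 99 can recover 99 − 86 = 13 of these. For someone who withdraws between Week 10 and the Week 12 visit, the latest review is Week 10 (Day 71), level with the last FP dose, so it adds nothing. Both Day 86 and the true date lie between Week 12 and Week 16, so the secondary-estimand probabilities tabulated at 4, 8, 12 and 16 weeks do not change.

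**The case against.** Three arguments can be made for the event list as it stands.

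- *The omission may be deliberate.* Section 7.2.3 justifies the secondary estimand here by missing data after withdrawal, which the discontinuation event covers. But the text names the Section 7.1.4 estimand without restriction and records no departure from it.
- *Deviators may not count as successful completers.* The SAP does not define success, so censoring them is the natural reading and not an express statement. The alternative leaves them neither event nor censored, which 7.2.4.1 does not allow.
- *The reach is limited.* This stands. It concerns one version of one secondary endpoint, and nothing in the SAP shows that deviations differ by arm.

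A reader might infer more than the documents support.

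- *That the worst-case estimand fails altogether.* It does not. The binary estimand in 7.1.4 includes all five situations.
- *That visit windows alone make adherent participants non-compliant, because "Planned Treatment Duration is defined according to the schedule of activities".* That requires compliance to be computed for each FP dose step. Section 12.6.2 specifies cumulative compliance for each background therapy. In-window adherent participants then score 12/14 to 16/14 (86% to 114%) on FP/SAL and 51/56 to 61/56 (91% to 109%) on FP, inside the limits.
- *That event dates are wrong in general.* Loss-of-control dates come from the log page, completers are censored at Day 113, and other-reason withdrawals in the first 10 weeks use the FP/SAL or FP stop date.
- *That the early-withdrawal visit or last ACQ-5 should date the withdrawal.* Participants restart ICS/LABA at once on withdrawal, so either could count time on restarted therapy as event-free. A review date is not a withdrawal date; it only shows how long control was documented.

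**Conclusion.** The event list in 7.2.4.1 contradicts the estimand it invokes: two of the five worst-case situations are missing. This follows from the text alone. The size does not. The gap of about 1 to 10 participants per arm of 70 depends on the assumed 2% to 20% deviation share and on the planning proportions. With equal shares, the binary worst-case ratio moves towards 1 (0.65 to 0.77, against 0.64) while the Kaplan-Meier version stays put. That is a loss of consistency and conservatism, not a demonstrated bias between arms.

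The dating point is real but small. It affects withdrawals after the Week 12 infusion for reasons other than loss of control or AE/SAE/death, by at most 26 nominal days. It reaches the log-rank test, possibly the quartiles, and event-free follow-up in the primary estimand.

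**What to change.** In Section 7.2.4.1, add both intercurrent events to the secondary-estimand event list and take the earliest qualifying date. State the dates:

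- LoAC and TIT deviations: the deviation start date.
- Compliance below 80% or at least 120%: an explicit convention, because a cumulative percentage has no onset. One option is the end date of the background therapy concerned. On nominal days this places such events at Day 15 (FP/SAL) or Day 71 (FP), which should be footnoted in Table 2.13 and Figure 2.10.

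If the narrower event list is intended, give it a different estimand name and record the departure from 7.1.4.

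In Section 12.6.2, for other-reason withdrawals between Week 10 and Week 16, use the latest scheduled review documented as free of loss of control and before ICS/LABA restart, when that is later than the derived date.

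The cost is SAP wording, two derivations and a rerun of the affected displays. This assumes that the deviation dataset holds start dates and that ICS/LABA restart dates can be taken from the concomitant medication records; the SAP confirms neither. No change to trial conduct is needed.

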### Model Checking & Diagnostics

- None

### Model Results Presentation

- Kaplan-Meier plots of the probability of a participant experiencing loss of asthma control by treatment will be produced.
- In addition, a summary table will be produced showing the probability of experiencing loss of asthma control by 4, 8, 12 and 16 weeks along with the median, upper and lower quartiles of time to loss of asthma control on both treatment arms (this will be NA if <50% of participants on a treatment lose control).

### Endpoint / Variables

- Change from baseline in pre-bronchodilator FEV1 at Weeks 2, 4, 6, 8, 10, 12, 14, 16.

### Strategy for Intercurrent (Post-Randomisation) Events

Primary estimand only.

### Model Specification

Only data until Week 4 (down titration of ICS) will be analysed, all data post Week 4 will be summarised descriptively only.

Data up to and include Week 4 (down titration of ICS):

A repeated measures model with terms for baseline FEV1, treatment, visit and screening eosinophil strata. The model will also include baseline FEV1 by visit, visit by treatment and screening eosinophil strata by visit interactions.

Model Structure:

- The variance-covariance matrix will be assumed unstructured.
- Kenward Roger (KR) method will be used for calculating degrees of freedom. If the analysis does not run using the KR method then the residual method will be used instead.
- An observed margins (OM) dataset will be used to derive the LS means using coefficients which are based on the subjects used in the analysis. This is a dataset with a row for every subject-visit combination that contains all of the covariates. The OM will be at the average baseline FEV1.

FEV1 at Weeks 4 Only - Fractional Polynomials (Exploratory Analysis):

- Screening blood eosinophil count will be transformed using a first order fractional polynomial term, and then a second order fractional polynomial term which will be included in the model as a continuous covariate. A treatment group by transformed eosinophil covariate interaction will also be included in the model to allow the magnitude of the treatment difference to differ by

screening eosinophil count.

- The impact of extreme observations are a well-known problem with fraction polynomial modelling. To address this a two-step transformation to “pull-in” extremes and shift the origin away from zero will be used (Royston and Sauerbrei, 2007). The formula to achieve this is given below:

$$g\delta(x) = \delta + (1 - \delta) \frac{g(x) - g(x_{(\delta)})}{g(x_{(n)}) - g(x_{(\delta)})}$$

$$\text{where } g(x) = \left[ \ln \left( \frac{\Phi\left(\frac{(x-\bar{x})}{s}\right) + \varepsilon}{1 - \Phi\left(\frac{(x-\bar{x})}{s}\right) + \varepsilon} \right) + \varepsilon^* \right] / (2\varepsilon^*)$$

with:  $0 < \delta < 1$

$$\varepsilon = 0.01$$

$$\varepsilon^* = -\ln [\varepsilon / (1 + \varepsilon)]$$

$$\bar{x} = n^{-1} \sum x_i$$

$$s = (n - 1)^{-1} \sum (x_{(i)} - \bar{x})^2$$

As recommended we shall use  $\varepsilon = 0.01$  and  $\delta = 0.2$ .

- All models (first and second order) will be evaluated and the best fitting model will be selected based on the AIC.
- The selected best fitting model will be used to predict FEV1 by treatment arm along with the corresponding predicted difference in FEV1 by screening eosinophil count. This model will include the OM option which will use the analysis dataset.
- The fit of the model to the raw data will be assessed visually by overlaying a plot of the treatment estimates and differences estimated in groups defined by quartiles of screening eosinophil counts. Estimates will be plotted against the mean eosinophil count within each subgroup.

### Model Checking & Diagnostics

- Distributional assumptions underlying the model used for analysis will be examined by

obtaining a normal probability plot of the residuals and a plot of the residuals versus the fitted values (i.e. checking the normality assumption and constant variance assumption of the model respectively) to gain confidence that the model assumptions are reasonable.
Model Results Presentation

 
The estimates of the mean and difference for each treatment group from the model will be produced, along with 95% confidence intervals and p-values for treatment comparisons.
 

Endpoint / Variables

 
Change from baseline in fractional exhaled nitric oxide (FeNO).
 
Change from baseline in blood eosinophils
 

Strategy for Intercurrent (Post-Randomisation) Events
Primary estimand only.
Model Specification

Only data until Week 4 (down titration of ICS) will be analysed, all data post Week 4 will be summarised descriptively only. Both FeNO and eosinophils have the ratio of post-baseline values to baseline values log transformed prior to analysis. For FeNO where multiple measurements can be taken at a visit, the data will be log transformed (using the natural logarithm (ln) hereby referred to as log) and the average log transformed value used as the visit value.
 
FeNO Analysis Model: A repeated measures model with terms for log(baseline FeNO), treatment, visit, screening eosinophil strata and interaction terms for log(baseline FeNO) by visit, treatment by visit and screening eosinophil strata by visit.
 
Eosinophil Analysis Model: A repeated measures model with terms log(baseline eosinophils), treatment, visit and interaction terms for log(baseline eosinophils) by visit and treatment by visit.
 
Model Structure:
 
 
The variance-covariance matrix will be assumed unstructured.
 
Kenward Roger (KR) method will be used for calculating degrees of freedom. If the analysis does not run using the KR method then the residual method will be used instead.
 
An observed margins (OM) dataset will be used to derive the LS means using coefficients which are based on the subjects used in the analysis. This is a dataset with a row for every subject-visit combination that contains all of the covariates. The OM will be at the average logarithm of baseline FeNO or average logarithm of baseline eosinophils dependent on the model.
 
 
Due to a large amount of FeNO data being outside the normal range, further analysis of FeNO may be explored.

Model Checking & Diagnostics

 
Distributional assumptions underlying the model used for analysis will be examined by obtaining a normal probability plot of the residuals and a plot of the residuals versus the fitted values (i.e. checking the normality assumption and constant variance assumption of the model
 

respectively) to gain confidence that the model assumptions are reasonable.

